- **Visual Spatial Memory Learning Test** Cannabis can affect memory acutely. Variation in some aspects of cognitive performance has been found to be moderately and positively correlated with some individual aspects of the SFST; particularly among tasks which assess reaction time. Impairment of these cognitive processes can also contribute to the completion of complex tasks such as driving or the SFST. We will assess short term memory using a visual-spatial learning test (VSLT). This test is modeled after other tests of visuospatial memory (e.g., the Brief Visuospatial Memory Test-Revised, Visual Spatial Learning Test). The test requires the subject to a) memorize 5 designs that are difficult to verbally encode, b) recognize them among a group of 15 designs (8 foils) and c) recall the correct placement of these designs on a 6 X 4 matrix. Participants will complete one trial. The score is the number of figures correctly identified and placed. (2 minutes).

Assays for Δ9-THC in Plasma

For purposes of correlation with the above findings, serum levels of THC will be determined hourly. Blood will be collected in grey top (NaF) tubes and then the tubes inverted 8-10 times to mix. EDTA plasma will be processed as soon as possible after collection. The tubes will be centrifuged at 400xg for 10 minutes to separate plasma and cells and then, using a transfer pipette,

plasma will be removed carefully to avoid disturbing the cell layer. The plasma will be transferred to 1.8 ml cryovials and stored as plasma aliquots at -70C.

$\Delta 9$ -THC and metabolites will be quantified using isotope dilution ultra-performance liquid chromatography (UPLC) and tandem mass spectrometry (MS/MS) using methodologies similar to what have been published. Briefly, deuterium labeled internal standards will be added and proteins will be precipitated using acetonitrile. $\Delta 9$ -THC and CBD will be isolated using solid phase extraction and analyzed using electrospray ionization. $\Delta 9$ -THC will be analyzed using positive ion electrospray while negative ion ESI will be used for CBD using Waters Xevo TQS equipped with Waters Acquity UPLC. The limit of quantification (LOQ) will be 0.5 ng/mL of each of the components in whole blood. Our laboratory at UCSD has been using similar methodologies to accurately quantify small molecules for many years (39).

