4. ESTIMATED DURATION OF THE STUDY

We estimate that the study will take 4 years.

5. LAY LANGUAGE SUMMARY OR SYNOPSIS (no more than one paragraph)

This study will involve treating low back pain associated with nerve injury with two types of medicinal cannabis for eight weeks. Research subjects will consume either oral Δ9-THC (dronabinol), vaporized 4.0% Δ9-THC/6.5% CBD (estimated percentages), or placebo. An analysis will then be performed to assess the risk-benefit ratio of dronabinol and vaporized 4.0% Δ9-THC/6.5%. In addition, subjects will undergo driving simulation to determine how long it takes for them to recover from these medications.

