If already using cannabis, participants will be asked to slowly taper cannabis use over a one-week period (Baseline Week - Figure 1) so that they are only using study medications during the remaining 10 weeks of the clinical trial. If unable to abide by this, subjects will not be allowed to participate in the study. Participants will be asked to abstain from cannabis 7 days prior to study entry. In order to ensure abstinence, we will use the Draeger 5000 saliva screening test for tetrahydrocannabinol at their first experimental visit to ensure that they have adhered to this period of abstinence before the study. A level above 5 ng/ml will indicate recent use and the appointment will be rescheduled.

Baseline Period:

If eligibility criteria (see below) are met, subjects will be instructed on completing a paper diary (Appendix 4). Provided their VAS pain intensity remains above 3/10 during the Baseline Week, they will be given oral and herbal study medication (and a Volcano Vaporizer) at the next study visit one week later.

At the baseline visit, participants will be given the Beck Depression Inventory (BDI-II) in order to screen for depression and suicidality. They will also be given the AUDIT and DAST to screen for substance use problems. The PSQ and Mood Disorder Questionnaire will also be administered to screen for Schizophrenia and Bipolar Type I, respectively. The painDETECT Questionnaire will be administered to distinguish neuropathic low back pain from non-neuropathic low back pain. The Survey of Cannabis Use will be administered during this period to obtain information on the cannabis use habits of the participant.

Should the participant choose to participate in the driving simulation portion of the study, the Driving History and Habits Questionnaire will be administered to obtain information on participant driving history, should they decide to participate in the driving simulation study portion.

Telephone Interview:

To determine eligibility, each prospective participant will be asked the following questions from the NIH Chronic Low Back Pain Definition:

1. Do you have low back pain?

No	STOP.....	0
Yes		1

2. How long has low back pain been an ongoing problem for you?

Less than 1 month	0
1-3 months	1
3-6 months	2
6 months -1 year	3
1-5 years	4
More than 5 years	5

3. How often has low back pain been an ongoing problem for you over the past 6 months?

[figure not shown]
Every day or nearly every day in the past 6 months	0

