- Behavior Notes Instrument: The clinician will fill this out during Neuropsychological testing to note confound variables associated with participant during the appointment.
- Adverse Events Form: A form to be filled out by the clinician that records any adverse events that have occurred since the last appointment due to study medication.

NIH Task Force on CLBP Impact Score

The impact score is a novel combination of 3 constructs; pain intensity, interference, and function. It is assembled in the Repeated Measures Recommended Minimal Dataset (Appendix 9).⁹

Pain Relief

Neuropathic Pain Scale: This instrument has an ordinal scoring of one to ten for several characteristics of neuropathic pain.^{10, 11} Specifically, the responses measure pain characteristics such as intensity, sharpness ("like a knife"), burning ("on fire"), aching ("like a bruise"), cold ("freezing"), sensitivity ("like raw skin"), itching ("like poison oak"), unpleasantness ("intolerable"), and the amount of deep versus superficial pain. (5 minutes)

Mood Evaluation

Profile of Mood States (POMS): The POMS measures six identifiable mood or affective states: 1) Tension-Anxiety 2) Vigor-Activity 3) Depression-Dejection 4) Fatigue-Inertia 5) Anger-Hostility 6) Confusion-Bewilderment. The POMS can be re-administered on a weekly basis, which is long enough to detect the respondent's mood responses to his or her current life situation, but short enough to assess acute treatment effects. Sixty five items rated from 0 to 4 and scored in terms of total mood disturbance.¹² (10 minutes)

Beck Depression Inventory-II (BDI-II): The BDI-II is a twenty-one item depression scale in which participants can rate depressive symptoms and attitudes from 0 to 3 in terms of intensity.¹³ We will measure clinical depression using the BDI-II and will include this measurement in analyses to provide an adjusted view of analgesia and side-effects. (3 minutes)

Neuropsychological Testing

WAIS-III Digit Symbol test: a test of concentration, psychomotor speed, and graphomotor abilities. This pen and paper test involves having subjects substitute a series of symbols with numbers as quickly and accurately as possible during a 120 second period. The results are expressed as the number of correct substitutions.¹⁴ (10 minutes).

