10. HUMAN SUBJECTS

Total number of participants to be enrolled: This will be a single site study with 120 participants enrolled at UCSD.

Age: Because of the problems inherent in the use of cannabis in children and adolescents, we will not enroll individuals below the age of nineteen. Frequent use can affect school performance and relationships with family members in younger individuals ^{42, 43}. Earlier and greater involvement with marijuana has also been associated with increased risk of poor mental health ^{44, 45}.

Gender: Both male and female populations develop chronic low back pain (CLBP); however, there is a tendency towards a higher incidence in males.

Ethnic background: CLBP is ubiquitous. Global studies have shown that low back pain is one of the most common complaints that patients bring to their physicians ^{46, 47}. Given the diverse ethnic background of San Diego, we should be able to recruit subjects from multiple ethnic backgrounds. A neuropathic component has been found in approximately 37% of patients with CLBP ⁴⁸; given the relative frequency of the latter, we should not encounter difficulty recruiting 120 participants.

Health status: Individuals with significant cardiovascular, hepatic or renal disease, uncontrolled hypertension, and chronic pulmonary disease (eg, asthma, COPD), will be excluded. This will be operationalized using criteria from the literature on adverse effects of medicinal cannabis ^{49, 50}.

Inclusion criteria

- Age greater than 18
- Presence of chronic low back pain (CLBP) defined as the response to two questions 1) How long has back pain been an ongoing problem for you? 2) How often has low back pain been an ongoing problem for you over the past 6 months? A response of greater than 3 months to question 1 and a response of "at least half the days in the past 6 months" to question 2 will define CLBP according to the NIH Task Force on Research Standards for Chronic Low Back Pain (Appendix 15). ⁹
- Visual average numerical pain intensity greater than 3/10 during one-week observation period
- To avoid confounding by concurrent medications and/or prior cannabis exposure, participants will have had a stable analgesic regimen that they will continue throughout the study and not having used cannabis for more than 7 days prior to study entry. The latter criteria will be verified by the use of the Draeger test at the first experimental visit.

Exclusion criteria

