5.1 Power Estimation

Power estimates for each outcome assumed a 5% significance level. Totally, N=120 subjects will be randomized in 1:1:1 ratio to the three treatment arms, that is, 40 subjects to each arm. Using the same 16% drop-out rate experienced in our previous study and that 87% of the completers possess a valid driver's license, a national average published by the Department of Transportation, power was calculated for 33 subjects per treatment arm (total N=99) for Aims 1 and 2, and 29 subjects per treatment arm (total N=87) for Aim 3. We have 80% power to detect effect sizes equivalent to Cohen's $d=0.54$ and $d=0.58$ for sample sizes 33 and 29 respectively. This effect size is based on differences between groups of changes from baseline at the end of the study (week 8). The power is calculated using specific formulas for a time-by-treatment interaction in a longitudinal linear mixed-effects model {Diggle PJ, Heagerty P, Liang KY, Zeger SL: Analysis of Longitudinal Data, 2nd edition, 2002, Oxford University Press, Oxford, p.29}. Power is expected to be higher for larger effect sizes and fewer dropouts.

6. Data and Safety Monitoring Committee (DSMC)

Progress reports will be presented to the DSMC every 6 months. Two reports (open and closed reports) will be generated and presented in two sessions.

Key study personnel and all DSMC members will attend the open session; *the open report* will present data in aggregate form (not by arm). Open session attendees will review presented summarized data for data completeness and accuracy (e.g., review ranges for numeric variables to catch any outliers/unusual observations).

The closed session will include only the study statistician and members of the DSMC; *the closed report* will present data by treatment arm, but in blinded fashion,

i.e., arms will be presented as arm X, arm Y, arm Z. Treatment labels can be revealed to the DSMC members upon their request if major concerns arise. Statistical comparison of relevant characteristics between the arms will be done. No interim analysis comparing primary outcomes between the arms will be performed in order to preserve the power of the primary analysis and the overall Type I error at 0.05 level till the end of the study, unless requested by the DSMC. Members of the DSMC will be asked to maintain confidentiality related to the interim data presented in the closed report until the end of the trial.

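### No SAP analysis uses the baseline painDETECT score or adjusts pain for BDI-II, and the lay synopsis names a narrower population than the trial enrols

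*Protocol*

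**What the plan says.** **Population.** The lay synopsis (Protocol section 5) reads: "This study will involve treating low back pain associated with nerve injury with two types of medicinal cannabis for eight weeks". The grant title in section 22 also refers to neuropathic low back pain. The project title, the inclusion criteria and SAP section 1 refer to chronic low back pain without that restriction. The key criterion is "Presence of chronic low back pain (CLBP) defined as the response to two questions", and those questions concern duration and frequency. No inclusion or exclusion criterion requires a neuropathic component or sets a painDETECT cut-off. Section 10 remarks, in support of recruiting 120 people, that "A neuropathic component has been found in approximately 37% of patients with CLBP".

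**painDETECT.** Under Baseline Period in Protocol section 9: "The painDETECT Questionnaire will be administered to distinguish neuropathic low back pain from non-neuropathic low back pain". The SAP never names the instrument, whether as covariate, stratum, subgroup variable or listed baseline characteristic.

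**BDI-II.** Under Mood Evaluation in Protocol section 9, the investigators say they "will include this measurement in analyses to provide an adjusted view of analgesia and side-effects". SAP 4.2 lists BDI-II as a secondary outcome. SAP 4.3.3 plans a mediation analysis linking pain effects to mood. No model for pain carries BDI-II as a covariate.

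**Primary model.** SAP 4.1.1 treats time as a six-level factor that includes baseline and drops the arm main effect, on the assumption of equal baseline means. The primary contrast is vaporized cannabis (A) versus dronabinol (B). A versus placebo (C) is secondary and B versus C exploratory.

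**The concern.** A reader of the synopsis would think the result applies to nerve-injury back pain, whereas the criteria admit people with no neuropathic component. The instrument that would describe the mix is collected before treatment, but the SAP gives it no role, not even in a baseline table. The promised BDI-II adjustment is likewise not carried into any pain model.

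The team's own earlier clinical trials (Protocol sections 7 and 18) were in neuropathic pain, and section 18 says it is not known whether chronic low back pain will respond. Whether benefit depends on a neuropathic component is thus an obvious question after any result, particularly a null one. Without a prespecified analysis the answer would come from post hoc work, with free choice of cut-off, contrast and covariates.

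**Working it through.** **Inputs.** From SAP 5.1: 5% level (sidedness not stated; two-sided assumed), 80% power, d=0.54 with 33 completers per arm and d=0.58 with 29, using a time-by-treatment formula. From SAP 4.1.1: weeks 0, 1, 3, 5, 7, 8. From Protocol section 10: 37% neuropathic share of chronic low back pain in general. Assumed: within-subject correlation ρ=0.5, which the SAP does not state.

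**1. Reproduce the plan's power.** The mean week is 24/6 = 4, so Sxx = 16+9+1+1+9+16 = 52, and the range R is 8. The variance factor is v = (1−ρ)R²/Sxx = 0.5 × 64/52 = 0.615. Power = Φ(d/√(2v/n) − 1.96).
- n=33, d=0.54: SE = √(2×0.615/33) = 0.193; 0.54/0.193 = 2.80; power 79.8%.
- n=29, d=0.58: power 80.4%.

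Both figures reproduce. The first would be 65.7% at ρ=0.3 and 95.1% at ρ=0.7. A plain two-sample calculation (v=1) gives 59.2%.

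**2. Illustrate dilution.** Suppose the contrast has d=0.54 in neuropathic participants and exactly 0 in the rest. With share p the pooled effect is 0.54p.

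| Share p | Pooled d | Power, SAP scale | Power, plain two-sample |
|---|---|---|---|
| 20% | 0.108 | 8.1% | 6.4% |
| 37% | 0.200 | 17.7% | 12.5% |
| 50% | 0.270 | 28.7% | 19.4% |
| 75% | 0.405 | 55.5% | 37.6% |
| 90% | 0.486 | 71.1% | 50.6% |
| 100% | 0.540 | 79.8% | 59.2% |

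At p=37% on the SAP scale, ρ also matters:
- ρ=0.3: v=0.862, SE=0.228, power Φ(0.87−1.96), about 14%.
- ρ=0.7: v=0.369, SE=0.150, power Φ(1.34−1.96), about 27%.

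**3. What an arm-by-painDETECT analysis could show.** Take a 37%/63% split of 33 completers per arm, 12.2 and 20.8, as a binary stand-in for the continuous score.
- Interaction SE, plain scale: √(2/12.2 + 2/20.8) = 0.51 SD.
- Interaction SE, SAP scale: 0.51 × √0.615 = 0.40 SD.
- Power for a 0.54 difference between strata, SAP scale: Φ(0.54/0.40 − 1.96) = 27%. The difference detectable with 80% power is 1.12 SD.
- Within the neuropathic stratum alone, power for d=0.54 is about 40%.

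**4. Baseline adjustment already present.** Because baseline pain is one of the time levels and the arms share a baseline mean, the SAP 4.1.1 model already uses baseline pain. The added covariates can gain only what they explain beyond it, and no figure in the documents allows that to be estimated.

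**The case against.** Several stronger readings are tempting, and the documents do not support them.

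- **That this is by definition a neuropathic pain trial.** The project title, study rationale, eligibility criteria and SAP consistently say chronic low back pain, and the specific aims name no neuropathic restriction. The synopsis is one lay sentence. The grant title also says cross-over, which this parallel trial is not, so it looks like legacy wording.
- **That a neuropathic-specific effect could not be seen.** painDETECT is collected before treatment, so a post hoc analysis remains possible. What is missing is a planned one.
- **That the trial has 18% power.** That is one point in a conditional range. It needs zero effect in everyone else, and the 37% describes chronic low back pain generally; the enrolled share is unknown. The primary contrast compares two active arms, so dilution reaches it only if the A−B difference is itself confined to neuropathic pain. The placebo contrasts are more directly exposed.
- **That supporting evidence is only neuropathic.** The cited comparison of inhaled cannabis with dronabinol (Protocol section 7) was a cold-pressor experiment, and both reduced pain.
- **That the primary model ignores baseline.** It does not, as shown above.

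It is also fair to say that SAP 2.1 could include painDETECT among unlisted baseline characteristics, and that a weak interaction estimate will rarely separate a null result from an unsuitable population.

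What stands is the mismatch in the synopsis, the absence of any planned use of painDETECT, and the undelivered BDI-II adjustment. Mediation through mood does not meet that promise: it asks whether treatment works through mood, not what the treatment effect is at a given baseline mood.

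**Conclusion.** The point holds as a gap between protocol and SAP, not as a flaw that invalidates the primary comparison. The synopsis should match the criteria, and two baseline measures should get the analysis their stated purpose implies. The precision benefit is probably modest and cannot be quantified from the documents.

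The dilution figures (8% to 71% power for shares of 20% to 90%) show why the question is worth planning for. They rest on an effect confined to neuropathic pain, ρ=0.5 and two-sided testing; they do not predict this trial's power. Using painDETECT would make the question visible without making the trial powered to answer it.

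**What to change.** 1. **Protocol section 5:** say that chronic low back pain with or without a neuropathic component is enrolled, and note that the grant title in section 22 differs.
2. **SAP 4.1.1:** add a prespecified adjusted analysis of pain with baseline BDI-II and the continuous baseline painDETECT score as covariates, each with its time interaction. Use only the pre-treatment BDI-II value, since later values may be affected by treatment.
3. **SAP 2.1:** tabulate painDETECT by arm.
4. **SAP 4.3, optional:** prespecify an exploratory arm × painDETECT estimate (continuous score) for weeks 5-8, with a 95% CI for each of A−B, A−C and B−C, labelled as estimation only and reported whatever its p-value. The continuous score avoids choosing a cut-off.

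The cost is wording, since both instruments are already given at baseline. Statistically it is two coefficients per time level (2 × 6 = 12 in all) and an imprecise exploratory estimate. The change has full value only if made before unblinding.

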Cannabis Withdrawal Scale: The Cannabis Withdrawal Scale can be used as a diagnostic instrument in clinical and research settings where monitoring of withdrawal symptoms is required.²² This will be performed after the 2-week tapering period has concluded. (10 minutes) If there was a previous adverse event or events (AE(s)), the Cannabis Solicited Adverse Events instrument will again be administered to ensure that the AE(s) have resolved. Participants will continue to be followed until there is resolution of the AE(s).

ARM #2. Driving Simulation:

Subjects with drivers’ licenses will be scheduled for two experimental visits; one before they begin the randomized controlled trial, and a second visit after finishing their 8th week treatment. The initial visit will involve a 20-minute session to garner baseline values for driving skills. This visit will coincide temporally with the first session for the randomized controlled trial prior to Week 1 (Appendix 12).

At the time of the second driving simulation visit, subjects will be assigned the same medication that they have been using during the randomized controlled trial. Using a Volcano Vaporizer, subjects will inhale the average number of puffs they had consumed per session throughout the four previous weeks of the randomized controlled trial. They will use the Vaporizer before Hour 2 and again before Hour 6 (Table 3). They will also take the same oral medication that was provided during the randomized controlled trial. In addition to examining the effects on driving simulation, acute effects of study medications on spontaneous pain and vital signs will be determined (Appendix 13). We will administer the simulator sickness assessment during the first 2 hours of the appointment to ensure that the participant is physically able to perform the driving simulation tasks.

At the beginning of driving simulation appointments, participants will be given a urine toxicology and a breathalyzer test to test for any illicit substances that is not prescribed by a physician. Should the participant screen positive for an illicit substance, they will either be asked to reschedule or be discontinued from the study at the Principal Investigator's discretion. If this happens, participants will be compensated \$10 for arriving to the scheduled appointment.

During the Driving Simulation study visit, the participants will be given paper and pencil forms that measure the following:

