15. RISK MANAGEMENT PROCEDURES AND ADEQUACY OF RESOURCES

At every study visit, stopping criteria will include:

Pulse: an irregular pulse or pulse rate > 110 beats per minute

Blood Pressure: systolic blood pressure > 180 mmHg or diastolic > 110 mmHg

Respirations: respiratory rate > 20 breaths per minute

Pulse: an irregular pulse or pulse rate greater than 110 beats per minute will result in cessation of participation and, if deemed advisable by a study clinician, transfer to the emergency department (across the street from our research center).

Blood Pressure: If the systolic blood pressure is ≥ 160 to < 180 mmHg or the diastolic is ≥ 100 to < 110 mmHg, a study clinician will conduct an evaluation to see if the participant has symptoms that would mandate discontinuation. Examples would include severe headache, confusion, chest pain, dyspnea, irregular heartbeat, and/or palpitations. Final determination regarding possible discontinuation will be made by a study investigator. If discontinued from the study, the participant will be asked to have their blood pressure evaluated by their primary care physician as soon as possible. If the systolic blood pressure is > 180 mmHg or the diastolic is > 110 mmHg, the participant will be discontinued from the study and either be transferred to the emergency department or be asked to visit their primary care physician as soon as possible. The end organ response to the blood pressure will guide the clinician's decision (e.g., the development of angina pectoris or hemiplegia will mandate transfer to the emergency department).

Respirations: shortness of breath will result in potential cessation of participation and possible transfer to the emergency department following evaluation by a study clinician, who will consult with the study investigator.

A locally developed self-report instrument, the Cannabis Solicited Adverse Events (Appendix 29) will be administered to assess distress from psychological effects of cannabis. This will be performed on a prn basis by the trained staff and routinely at the end of the acute

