administration session. The items on this instrument ask participants about experiencing anxiety, paranoia, and hallucinations. Excess intoxication will also be assessed using this instrument which asks participants about their having dizziness, drowsiness, confusion, emotional changes, and/or cognitive changes. Positive responses to these items, if Grade 2, 3 or 4 (see below for definitions), will result in notification of a study clinician who will speak with the participant to see if discontinuation of participation in the study would be in her or his best interest.

Using the Cannabis Solicited Adverse Events instrument mentioned above, an Adverse Events Form (Appendix 30) will be completed. Adverse events will be characterized as 1 = Mild, 2 = Moderate, 3 = Severe, and 4 = Life Threatening using the following definitions (consistent with those used by the National Cancer Institute):

GRADE 1 MILD	GRADE 2 MODERATE	GRADE 3 SEVERE	GRADE 4 POTENTIALLY LIFE-THREATENING
Mild symptoms causing no or minimal interference with usual social & functional activities with intervention not indicated	Moderate symptoms causing greater than minimal interference with usual social & functional activities with intervention indicated	Severe symptoms causing inability to perform usual social & functional activities with intervention or hospitalization indicated	Potentially life-threatening symptoms causing inability to perform basic self-care functions with intervention indicated to prevent permanent impairment, persistent disability, or death

Inasmuch as the scoring of Grades 2, 3, and 4 mention that an intervention is indicated, AEs with Grades 2 or 3 will be brought to the attention of a study clinician so that s/he may interact with the participant to determine if discontinuation of study participation is warranted. This will be done in consultation with an investigator. Grade 4 AEs will be managed by reports tendered to the FDA and the IRB within the required time limits specified by each organization. There will also be a determination of whether the AE is related, possibly related or not related to the study by the investigator for Grades 1 to 4.

Furthermore, the participant will be followed by the research team to insure that the AE(s) resolve. This might include recommending that the participant see their primary care physician (e.g., for a change in blood pressure medication).

Risks will also be mitigated using the following measures:

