2.2 Study enrollment, Randomization, and dropout

The 120 eligible participants will be randomized to Arm A (vaporized Δ9-THC (3.5%)/placebo oral pill, n=40), to Arm B (dronabinol/vaporized placebo THC, n=40), or Arm C (double placebo, n=40). With a 16% dropout rate, we expect 33 subjects completing the 8-week visit for each arm. The completers who have a valid driver's license will implement driving simulation. The number (%) of subjects randomized, number (%) of subjects completing the 8-week-treatment, and number (%) of patients lost to follow-up will be summarized overall and by treatment arm. Fisher's exact test will be used to compare the arms in the proportions of lost to follow-up. Reasons (if known) for lost to follow-up will also be recorded. The comparisons are following an order of importance: arm A vs. arm B; arm A vs. arm C; arm B vs. arm C. Since the three comparisons have different levels of importance, no correction will be done for multiple comparisons.

The dropouts and completers will be compared, overall and stratified by treatment arm, with respect to their baseline demographics, medical characteristics, and the prevalence and timing of adverse events. The statistical analysis will use Fisher's exact test for binary and nominal variables, Student's t test or Wilcoxon rank-sum test for continuous variables, and log-rank test for time-to-event analysis, censored at the time of dropout.

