3.1 Adverse events

The number (%) of subjects with adverse events will be tabulated and summarized overall and by treatment arm, with the grade of the adverse event (1-4) included. The study week and reasons for adverse events will be included. Using the Kruskal-Wallis rank sum test, the number of adverse events per individual and maximal grade for each individual were compared among the three treatment arms. The proportion of participants with severe adverse events (leading to permanent treatment determination) will be compared between treatment arms with Fisher's exact test using the strategy of the comparison described in 2.2.

4. Endpoints

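### The protocol gives two accounts of which adverse events are recorded, routine solicitation appears to reach only licensed completers, and SAP 3.1 does not say which events it compares

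*Protocol*

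**What the plan says.** Protocol section 9 lists the Adverse Events Form among the forms for repeated testing at study visits. The clinician completes it, and it "records any adverse events that have occurred since the last appointment due to study medication".

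Protocol section 15 describes the safety procedure differently. "Using the Cannabis Solicited Adverse Events instrument mentioned above, an Adverse Events Form (Appendix 30) will be completed", events are graded 1 to 4, and "There will also be a determination of whether the AE is related, possibly related or not related to the study by the investigator". The same section has the DSMB report summarise all adverse events as well as serious ones.

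On the timing of the solicited instrument, section 15 says: "This will be performed on a prn basis by the trained staff and routinely at the end of the acute" administration session. Section 9 adds a repeat after the taper, but on a condition: "If there was a previous adverse event or events (AE(s)), the Cannabis Solicited Adverse Events instrument will again be administered". Routine use at the six study visits is not stated.

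SAP 3.1 says that "the number of adverse events per individual and maximal grade for each individual were compared among the three treatment arms", by Kruskal-Wallis test. It also compares, by Fisher's exact test, the proportions with severe events that end treatment. It does not state whether events enter regardless of cause. SAP 6.1 and 6.2 head the safety items of the monitoring reports as study-related events. SAP 2.2 compares dropouts with completers on how often and when adverse events occurred.

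**The concern.** Two things are at stake.

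First, if the form is filled in as section 9 describes it, someone must judge causality before an event is written down. An event judged unrelated leaves no entry on the form. It cannot be reclassified later if a pattern emerges, and it cannot appear in the DSMB's summary of all events. The between-arm comparison then measures occurrence multiplied by attribution. If attribution differs between active and placebo arms, equal true rates produce unequal recorded rates.

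Second, the intensity of solicitation depends on how far a participant gets. A checklist that is routine only at one late session is not routine for people who leave early, or during titration in weeks 1 to 4, when those who cannot tolerate the minimum amounts are dropped and replaced. This second problem does not need any unblinding.

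The protocol's synopsis says the study will assess the risk-benefit ratio of the two active treatments, and adverse events carry much of the risk side.

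**Working it through.** **Which events are recorded.** No planned figure is at issue here, so the check is a comparison of texts.
- Section 9: the form covers events since the last appointment that are attributed to study drug.
- Section 15: each Grade 1 to 4 event is classed for relatedness, and one class is unrelated. This class would be empty if the section 9 restriction were applied first.
- Section 15, DSMB: a summary of all events. A form limited to attributed events cannot supply it.
- SAP 3.1: no causality rule. SAP 6.1 and 6.2: a heading that suggests a causality rule.

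The documents therefore support two different data sets for the same analysis.

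**Who is routinely solicited.** The only acute administration session described is the driving simulation visit. Section 9 text places it after week 8 and makes it optional. SAP 2.2 says: "The completers who have a valid driver's license will implement driving simulation". The title of Table 3 also mentions week 2, but the text schedules only one dosed driving visit. From SAP 5.1:
- Completers per arm: 40 × (1 − 0.16) = 33.6; the SAP uses 33.
- With a licence: 33 × 0.87 = 28.7; the SAP uses 29.
- Not reached: 40 − 29 = 11 of 40 per arm, including every dropout. Because the visit is optional, 29 is more likely high than low.

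SAP 2.2 then compares event frequency and timing between dropouts, none of whom has the routine checklist, and completers, most of whom do.

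**How large the attribution effect could be.** The documents give no adverse event rate and no attribution rate, so everything here is assumed. Each person has a Poisson number of events with true mean 1 in all three arms, with 40 per arm. A recorded event is a true event that was attributed, so recorded mean = 1 × attributed share. The three-arm Kruskal-Wallis test is run at 0.05 in 4,000 simulated trials.

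| Attributed share, active / active / placebo | Recorded means | Share of trials rejecting |
|---|---|---|
| all recorded | 1 / 1 / 1 | about 4.5% |
| 70 / 70 / 70% | 0.7 / 0.7 / 0.7 | about 5% |
| 80 / 80 / 70% | 0.8 / 0.8 / 0.7 | about 7 to 8% |
| 80 / 80 / 60% | 0.8 / 0.8 / 0.6 | about 16% |
| 80 / 80 / 50% | 0.8 / 0.8 / 0.5 | about 35% |
| 80 / 80 / 40% | 0.8 / 0.8 / 0.4 | about 61% |

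Under-recording that is equal across arms does not inflate error; only a difference between arms does. With equal shares in the two active arms, cannabis versus dronabinol stays at about 5% in every row.

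The result is sensitive to the count distribution. With overdispersed counts (negative binomial, shape 1, also assumed), the 16% falls to about 11% and the 61% to about 38%.

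An exact calculation on a simpler endpoint agrees in direction. It takes any recorded event, 40 versus 40, two-sided Fisher test at 0.05. With equal true risks of 40%, 60% or 80% and attribution of 80% versus 60%, rejection is 0.08, 0.14 and 0.24. It is about 0.03 when all events are recorded.

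**The case against.** The best defence is that section 9 offers a one-line description in a list of forms, whereas section 15 is the operative safety procedure and plainly expects unrelated events to be recorded. The form (Appendix 30) and the checklist (Appendix 29) are not in the documents, so nobody can say from them whether the form filters by cause or already has a relatedness field. This stands. A reader might infer that only attributed events are recorded, but the documents conflict on that and do not settle it.

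The form is also scheduled at study visits for everyone, so recording as such does not hinge on attending the driving visit; only routine solicitation does. Other channels exist: weekly telephone calls, a neurobehavioural screen for events between visits, vital signs, and repeated mood and intoxication scales. They do not replace an adverse event record, but it would be wrong to say that unattributed events necessarily escape all safety review.

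A reader might also infer that the people attributing events can often guess the arm. The documents do not show this. The trial is double blind with a placebo for each route, and no guess rate is given. The blinding questions go to participants after weeks 1 and 8, and none is described for clinicians. Section 7 reports that both active drugs raised subjective drug ratings over placebo in a laboratory study, which makes guessing plausible. It also reports minimal psychoactive effects in another study.

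Finally, the SAP ranks cannabis versus dronabinol first, and a tendency to attribute more events to active drug than to placebo touches that contrast least. It is not immune, since section 7 reports higher subjective ratings with marijuana than with dronabinol.

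**Conclusion.** The point holds as a conflict between sections 9 and 15, uneven routine solicitation, and an undefined event set in SAP 3.1. None of these needs an assumption about blinding, except that the reach of the routine checklist assumes the acute session is the driving visit.

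The bias in between-arm comparisons is conditional. It requires that the section 9 wording governs in practice and that attribution differs between active and placebo arms. Neither is documented. If both held, the placebo contrasts would be affected and the cannabis versus dronabinol contrast much less. The range from about 5% to about 61% shows only how strongly the result depends on unstated attribution shares; no single value in it should be read as an estimate for this trial.

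The change is worth making because events left unrecorded cannot be recovered at analysis.

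**What to change.** 1. In Protocol section 9, strike the final four words of the quoted description of the Adverse Events Form, and strike them from the form itself if they appear there, so that it agrees with section 15.
2. Record every adverse event since the last visit in all participants, with relatedness as a separate field in the three classes that section 15 already uses.
3. Give the existing solicited checklist at every study visit in all arms, on the same schedule, and keep the as-needed use and the acute-session use in addition.
4. In SAP 3.1, state that the all-causality set is the main comparison and that related events are a secondary summary. Align the headings in SAP 6.1 and 6.2, and let the dropout comparison in SAP 2.2 use the same set.

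The cost is a wording change in two documents, possibly one form, and a few minutes per visit.
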